## **2.2. Rationale**

Because of the progressive nature of congenital CMV-associated hearing loss, there is a large unmet medical need for treatment options beyond the neonatal period. Data from other CASG investigations support the study of antiviral treatment in infants and toddlers with CMV-associated hearing loss:

- Less than half of the hearing loss due to congenital CMV infection is present at birth.

- Children with congenital CMV continue to excrete virus in the urine for three to five years or even longer.
- The quantity of CMV (viral load) found in the urine and blood is greater in those children destined to develop hearing loss.
- CMV DNA has been detected in the perilymph of children up to four years of age undergoing cochlear implantation for CMV-induced hearing loss.
- Six weeks of IV ganciclovir at 6mg/kg bid given to neonates with congenital CMV disease beginning when they are less than 31 days of age reduces the future incidence of hearing loss.
- Six weeks of intravenous ganciclovir given to neonates with congenital CMV disease beginning when they are less than 31 days of age suppresses viruria, as detected by cell culture, but viruria returns promptly when the drug is stopped, even at the higher dose of 6mg/kg bid.
- The dose of oral valganciclovir that provides the same systemic exposure as the IV ganciclovir dose used in treatment of congenital CMV has been identified, with 16 mg/kg/dose of oral valganciclovir equaling 6 mg/kg/dose of IV ganciclovir.

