In the recently completed CASG 112 study of neonates and young infants with symptomatic congenital CMV disease, whole blood viral loads decreased from approximately 3.5 logs to under 2 logs in both groups over the course of the first six weeks of open-label valganciclovir therapy. Viral loads in the two groups of subjects then diverged initially following randomization, but by four months the group randomized to placebo had regained virologic control. By six months the two groups each had approximately 1.5 logs of virus detectable in blood, with the group that had received active drug throughout the six months then experiencing a rebound in viral load as treatment was stopped. Viral load was not assessed beyond month seven. Lower whole blood viral load area-under-the-curve during the first six weeks of therapy was associated with better hearing outcomes at 12 and 24 months in unadjusted ( $p=0.005$  and  $p=0.003$ , respectively) and adjusted ( $p=0.044$  and  $p=0.023$ , respectively) analyses. However, lower whole blood viral load area-under-the-curve from week six to month six was not associated with hearing outcomes in adjusted analyses ( $p>0.168$ ). This suggests that lowering systemic viral load initially aids in improving audiologic outcomes, but that the additional benefit of longer-term treatment for six months may relate to antiviral effects within the inner ear itself, where ongoing viral replication and damage may be impaired with prolonged antiviral therapy. We were not

able to identify specific breakpoints above which the viral load could be used as a biomarker for those patients at higher risk of developmental or hearing sequelae.

Furthermore, we will link this proposed study to the recently introduced national screening programs for hearing loss to demonstrate how CMV screening could be integrated into current diagnostic algorithms employed in the United States and United Kingdom, which offer a potentially cost-effective way to address the unmet medical problem of CMV.

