At each of the visits during the treatment phase (Study Days 1, 14, 28, and 42), safety labs will be assessed; viral load specimens from blood, urine, and saliva will be obtained; adverse events will be assessed; and concurrent medications will be recorded. Ganciclovir concentrations for population pharmacokinetic assessment will be obtained at each study visit while the subject is receiving study medication. Dose adjustments for weight change will occur at study visits during the subject's treatment period, and may also occur at any time during the treatment period as indicated per protocol for neutropenia, thrombocytopenia, or renal impairment. At the Study Day 70 visit, safety labs will be obtained; viral load specimens from blood, urine, and saliva will be obtained; adverse events will be assessed; and concurrent medications will be recorded. Hearing will be assessed at baseline and at Study Month 6.

Changes in whole blood viral load measurements will be correlated with hearing outcomes. In study subjects with increasing whole blood viral loads during the course of treatment, antiviral resistance may be evaluated. A Data and Safety Monitoring Board (DSMB) will be established to oversee the accrual, performance, safety, and efficacy of the trial.

**Study Day 1** of the study is the day following randomization that the first dose of study medication is administered. "Study drug" refers to valganciclovir or placebo (for six weeks). Follow-up visits referred to by Study Day will be determined by calendar day from Day 1 (e.g., if Study Day 1 is June 20, then Study Day 7 will be June 26); follow-up visits referred to by Study

Month will be determined by calendar month (e.g., if Study Day 1 is June 20, then Study Month 1 will be July 20).

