## **6.2. Dosage, Preparation and Administration of Study Intervention/Investigational Product**

Valcyte Powder for Oral Solution (valganciclovir) will be prepared by a licensed pharmacist in accordance with instructions in the package insert. Placebo for valganciclovir (Simple Syrup) will be transferred from the commercial bottle to identical empty amber bottles for dispensing.

Valganciclovir should be dosed at 16mg/kg body weight, unless specific dosage adjustment conditions have been met (see Section 6.3), administered orally twice daily for 6 weeks. Placebo for valganciclovir (Simple Syrup) should be dosed using the same volume that would be required for the active dose, administered orally twice daily for 6 weeks. Dose modifications for neutropenia, thrombocytopenia, renal impairment, and hepatotoxicity are detailed in Section 6.3.

Pharmacy preparation instructions for study product can be found in the protocol-specific Manual of Procedures (MOP), including directions for the reconstitution of the valganciclovir oral solution. Once reconstituted, the oral solution must be stored under refrigeration for no longer than 49 days. Valganciclovir oral solution has been shown not to adhere to syringes or to nasogastric tubing. Valganciclovir oral solution or placebo for valganciclovir should be administered into the patient's mouth by means of a syringe, which will be amber colored and provided by the study. If the patient is unable to swallow, the study product may be administered via the syringe through a nasogastric or gastric tube.

Study product administration should be timed to precede a feeding. If the subject vomits or spits up following the dosing, re-dosing will not be allowed.

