3.3 Derived variables

The primary efficacy assessment will be change in total ear hearing assessment between baseline and 6 months post enrollment. Categories used for hearing assessment of each ear for each time point will be normal hearing, mild hearing loss, moderate hearing loss, and severe hearing loss. Baseline and 6 month hearing categories will be compared and the change in each ear will be categorized into binary outcomes: Improved or no change versus Other (i.e., worsened) Note that the total ear assessment at each time point will be provided by the Independent Audiologist and entered in the database following the rules below and the information provided by the audiology reports.

In the model-based analyses, the “no change” category will be broken down into “Protected: normal to normal” as one category and “No Change: same degree of hearing loss at Baseline and Study Month 6” as another category. The rationale behind this is that if one is interested in the improvement of hearing loss, a subject that has normal hearing at baseline cannot improve further. Hence from an efficacy analysis point of view, the “Protected: normal to normal” can be viewed as protective effect of the drug from hearing deterioration. This analysis approach will be similar to the analysis of the previous CASG study that established the efficacy of 6 weeks of IV GCV in symptomatic congenital CMV disease with CNS involvement.

Analysis of actual viral load will be done using log base 10 transformation. Undetectable viral load value will be replaced by a value of 10. A summary measure of the viral load over time will be calculated two ways. The first approach considers all time points available by calculating the average area under the curve (AUC) (trapezoidal rule) applied to the log base 10 viral load. Average is based on the maximum period of time with viral load data for a given subject. To illustrate, if the calculated AUC for log₁₀ VL for a given subject is 200 from baseline to Day 70, then average AUC is $200/70=2.86$. Taking average AUC will enable us to use and compare data from subjects who did not have viral load values at the later time due to dropping out early, for example, with subjects with complete viral load data. The second approach is to take using difference between Month 6 and baseline log₁₀ VL. The last visit with available VL will be used for those without Month 6 VL. Section 11 contains more details on Viral Load analyses.

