4.1 General Study Design and Plan

[figure not shown]
(ICH E3;9)

The current study evaluates whether six weeks of antiviral therapy can stabilize hearing deterioration in older infants, toddlers, and young children who have developed CMV-associated hearing loss. This study is a Phase II, international, multi-center, double-blind, placebo-controlled evaluation of six weeks of valganciclovir treatment for children (up to 4 years of age) with virologically-confirmed congenital CMV infection and hearing loss.

Patients meeting inclusion/exclusion criteria will be offered enrollment into the trial. Randomization on the study occurs when the diagnosis of congenital CMV infection is confirmed, and the subject is then assigned to receive either 6 weeks of oral valganciclovir or 6 weeks of placebo. Study subjects will be stratified according to age at randomization (1 through 11 months, 12 through 23 months, 24 through 35 months, and ≥ 36 months) and CMV involvements (symptomatic and asymptomatic at birth) as a marker of disease severity. An independent Data and Safety Monitoring Board (DSMB) will oversee the conduct of the trial. During the course of their oversight, they may request to have access to unblinded data.

The target sample size is 54 subjects (27 in each arm). Up to 20% over-enrollment will be allowed to replace subjects who drop-out or who have inadequate audiology assessments. The primary endpoint will be change in total ear hearing assessments (improved + no change versus other) between baseline and 6 months. Secondary and tertiary endpoints will be assessments of other measures of hearing outcomes; detection of viruria, viremia, and CMV in saliva by PCR six weeks and six months after trial entry; the quantitative log reduction in viruria, viremia, and CMV viral load in saliva detected after six weeks of therapy; correlation of change in viral load with change in total ear and best ear hearing at six months; incidences of unanticipated medically attended visits and adverse events which lead to permanent discontinuation of valganciclovir therapy or have an unresolved outcome; and assessments of blood concentration of ganciclovir after administration of valganciclovir. Stopping rules will be employed in order to limit exposure of study subjects to a potentially unacceptable treatment.

Figure 1: Schematic of Study Design

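### SAP 3.3 allows an on-treatment viral load to stand in for Month 6, which can bias the viral load change variable

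*SAP*

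**What the plan says.** SAP 3.3 summarises viral load over time in two ways. The first is an average area under the log10 curve. For the other, "The second approach is to take using difference between Month 6 and baseline" log10 viral load. When Month 6 is missing, the rule is "The last visit with available VL will be used for those without Month 6 VL". No visit is excluded as a source. SAP 11, to which 3.3 refers for detail, adds no restriction, and the missing-data provisions in SAP 6.4 and 8.2 cover hearing only. The SAP expects some children to leave early: it justifies the average area by reference to "subjects who did not have viral load values at the later time due to dropping out early".

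Protocol section 4 places sampling inside the treatment period: "At each of the visits during the treatment phase (Study Days 1, 14, 28, and 42), safety labs will be assessed; viral load specimens" are taken then, and again at Day 70 and Months 4 and 6. Protocol 6.2 has study drug "administered orally twice daily for 6 weeks". Five post-baseline visits precede Month 6 (Days 14, 28 and 42, Day 70, Month 4), and three of them fall within treatment.

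The Month 6 change is used in Tables 30a to 31b, which relate it to change in total ear and best ear hearing (secondary endpoint 9). SAP 8.2 also plans a Wilcoxon comparison of log reduction between arms at 6 weeks and 6 months, without saying whether carried-forward values enter.

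**The concern.** Carrying a value forward assumes that it would have stayed where it was. That is hard to defend across the end of an antiviral course. A sample taken on drug reflects suppression; Month 6 is about 4.5 months after the last scheduled dose. Only active-arm children have drug suppression to carry forward, so the distortion falls on one arm.

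Protocol 2.2 gives grounds for doubt from earlier intravenous ganciclovir work: "viruria returns promptly when the drug is stopped". Protocol 5.4.6 makes the situation more likely, because a child whose therapy stops early has the next visit's evaluations on the day of discontinuation. If that child then leaves, the last sample dates from the end of drug exposure.

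What is at stake is the reading of viral load as a biomarker. Protocol 2.2 expects those data to be useful even if the hearing endpoint is not met, and to inform a later trial.

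**Working it through.** **The plan's own figure.** The only worked number in SAP 3.3 is the average area example: 200/70 = 2.857, which agrees with the stated 2.86. The plan gives no figure for the Month 6 change or for missing viral load.

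**Inputs.**
- On-treatment change in blood: Protocol 2.2 reports a fall from about 3.5 logs to under 2 over six weeks in an earlier study of neonates and young infants. This is taken as 2.0 − 3.5 = −1.5 log10.
- Arm size: 27 (SAP section 5).
- Share *s* of active children whose last viral load is on treatment: not given. It is varied over 5%, 10% and 20%. The top value borrows the ceiling in SAP 4.1, "Up to 20% over-enrollment will be allowed to replace subjects who drop-out" or have inadequate audiology, purely as an upper bound. The stated count of 10 gives 10/54 = 18.5%.
- True Month 6 change: not known for these children. Two cases are used. Full rebound (0) is an assumption suggested by the urine pattern. The blood course in the earlier study, about 1.5 logs at Month 6, gives 1.5 − 3.5 = −2.0.

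**Formula.** Bias in the active-arm mean = *s* × (on-treatment change − true Month 6 change).

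| *s* | Full rebound: *s* × (−1.5 − 0) | Earlier blood course: *s* × (−1.5 + 2.0) |
|---|---|---|
| 5% | −0.075 | +0.025 |
| 10% | −0.15 | +0.05 |
| 20% | −0.30 | +0.10 |

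Negative values overstate the reduction; positive values understate it. If only half of the children without a Month 6 value were last sampled on treatment, each entry halves. Since the earlier blood level at six weeks was below 2 logs, the fall exceeded 1.5 and the right-hand column is, if anything, too large.

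**Effect on a 6-month Wilcoxon test, if it uses this variable.** A simulation used 27 per arm, 20,000 runs, a two-sided 5% level, no true Month 6 change in either arm, an assumed SD of 1 log10, and a set number of active children shifted by −1.5.

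| Active children carried forward on treatment | False-positive rate |
|---|---|
| 0 | 4.7% |
| 1 | 4.7% |
| 3 | 6.6% |
| 5 | 11.2% |

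With 5 of 27 (18.5%), the rate is 17.0% at SD 0.5 and 8.4% at SD 1.5. One child moves the active mean by 1.5/27 = 0.06 log10, and two by 3.0/27 = 0.11.

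The effect on the odds ratios in Tables 30b and 31b was not computed. It depends on which children are affected and on their hearing results.

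**The case against.** A reader might infer that the error always runs toward a lasting antiviral effect. The documents do not support that for blood. In the earlier study, the children who stopped valganciclovir at six weeks were back under virologic control by four months and had about 1.5 logs at six months, no higher than the level reported at week six. On that course, carrying Day 42 forward would slightly understate the reduction. Protocol 2.2 does mention a group "then experiencing a rebound in viral load as treatment was stopped", but that was the group treated for six months, so it says nothing about Month 6 after a six-week course. Prompt return is documented only for urine, by cell culture. The 0.08 to 0.30 range therefore combines a blood figure with a urine pattern and is conditional, not an estimate. It also comes from younger, symptomatic children; Protocol 2.2 says the natural history in older children is undefined.

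Reach is limited as well. SAP 11 specifies the hearing association for whole blood, where direction is uncertain. To distort the main association, a child must have Month 6 hearing but no viral load at Day 70, Month 4 or Month 6. Most children who leave during treatment would lack both.

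These points stand, but they narrow the problem without removing it. Protocol 8.1.4 accepts clinical-care hearing results from 14 days before to 30 days after Month 6, against a visit window of ±7 days. Protocol 8.2 does not count unobtainable urine, or viral load blood missed through low volume or parental refusal, as a deviation. Hearing without viral load is therefore possible. Children who leave early enter the sensitivity analysis that sets missing hearing to worsened, where a carried low value would be paired with an imputed bad outcome; that would weaken a protective association.

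The SAP also has partial safeguards. The adjusted models in Tables 30b and 31b include therapy group, and Tables 28a to 29b use the average area instead. The average area is not immune, however: a child last sampled at Day 42 is averaged over treatment time only.

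**Conclusion.** The concern holds in a limited form. SAP 3.3 permits a drug-suppressed value to be analysed as Month 6, and no other section prevents it. The result can be a biased change variable in Tables 30a to 31b and, if the same variable is used, in the 6-month between-arm comparison.

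For urine, if the rule is applied there (SAP 3.3 does not limit it to blood), the bias would be toward a false lasting reduction. For blood it could go either way. Under an assumed 1.5 log10 fall and full rebound, it is 0.08 to 0.30 log10 for 5% to 20% of active children. The lower end is 0.05 × 27 = 1.35 children, so with only one or two affected the matter is negligible. If blood follows the earlier study, it is at most 0.10 log10 in the opposite direction. The deciding number, how many active children have no viral load after Day 42, is not in the documents.

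Neither the primary hearing endpoint nor the 6-week log-reduction endpoints depend on this rule.

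**What to change.** Delete the carry-forward sentence from SAP 3.3. For the association with hearing in Tables 30a to 31b, use observed Month 6 values. For a 6-month comparison between arms, use observed values or the Month 6 estimate from the mixed model already listed for Tables 24a to 24c, and state in SAP 8.2 which is meant.

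If a substitute is kept, at minimum do not carry Day 14, 28 or 42 values past the end of treatment, and add an observed-only sensitivity analysis. Reporting by arm how many children lack Month 6 viral load, with the visit of their last sample, would show whether the issue mattered.

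The rule does not appear in the final analysis plan of the protocol (section 11.4.2), so this is a SAP wording change. It costs a few children in one secondary analysis.

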4.1 General Study Design and Plan

[figure not shown]
(ICH E3;9)

The current study evaluates whether six weeks of antiviral therapy can stabilize hearing deterioration in older infants, toddlers, and young children who have developed CMV-associated hearing loss. This study is a Phase II, international, multi-center, double-blind, placebo-controlled evaluation of six weeks of valganciclovir treatment for children (up to 4 years of age) with virologically-confirmed congenital CMV infection and hearing loss.

Patients meeting inclusion/exclusion criteria will be offered enrollment into the trial. Randomization on the study occurs when the diagnosis of congenital CMV infection is confirmed, and the subject is then assigned to receive either 6 weeks of oral valganciclovir or 6 weeks of placebo. Study subjects will be stratified according to age at randomization (1 through 11 months, 12 through 23 months, 24 through 35 months, and ≥ 36 months) and CMV involvements (symptomatic and asymptomatic at birth) as a marker of disease severity. An independent Data and Safety Monitoring Board (DSMB) will oversee the conduct of the trial. During the course of their oversight, they may request to have access to unblinded data.

The target sample size is 54 subjects (27 in each arm). Up to 20% over-enrollment will be allowed to replace subjects who drop-out or who have inadequate audiology assessments. The primary endpoint will be change in total ear hearing assessments (improved + no change versus other) between baseline and 6 months. Secondary and tertiary endpoints will be assessments of other measures of hearing outcomes; detection of viruria, viremia, and CMV in saliva by PCR six weeks and six months after trial entry; the quantitative log reduction in viruria, viremia, and CMV viral load in saliva detected after six weeks of therapy; correlation of change in viral load with change in total ear and best ear hearing at six months; incidences of unanticipated medically attended visits and adverse events which lead to permanent discontinuation of valganciclovir therapy or have an unresolved outcome; and assessments of blood concentration of ganciclovir after administration of valganciclovir. Stopping rules will be employed in order to limit exposure of study subjects to a potentially unacceptable treatment.

Figure 1: Schematic of Study Design

Timing of study visits (days, months) for collection of urine, saliva, and blood (together with safety laboratory measurements at Study Days 1, 14, 28, 42 and 70)

During the 6 week treatment period and for 4 week thereafter, study subjects will be followed every two weeks for 6 weeks. Subjects will then be seen a month after the end of the treatment period, then at 4 and 6 months after randomization.

During the 6 week treatment period and at the 1 month post treatment period, safety labs will be checked and adverse events will be assessed. The dose of study medication will be adjusted for weight change at each of these study treatment visits, hence collection of growth parameters at each of the treatment visits. Whole blood will be obtained for CMV viral load at each of these visits as well. Hearing outcomes will be assessed at baseline and 6 months. Changes in whole blood viral load measurements will be correlated with hearing outcome.

Safety Reviews and Halting Rules

Halting rules for this study therefore have been constructed to interrupt study enrollment if an excessive number of subjects are experiencing neutropenia. Assuming that 75% of subjects receiving ganciclovir developed Grade 3 or 4 neutropenia and given that randomization is expected to be balanced between those in study drug and those in placebo, the stopping rule will be based on assuming that the overall event rate for all study participants (i.e., placebo and active subjects combined) is 37.5%. Therefore, study enrollment will be stopped and an ad hoc review will be performed if a significantly higher proportion (37.5%) of subjects in this study experience Grade 3 or Grade 4 neutropenia, as detailed in the following table:

X of the first Y subjects enrolled have Grade 3 or Grade 4 neutropenia, according to the table below. The stopping rules are based on the upper tail probabilities of the cumulative binomial with probability of an event set at 0.375. The cut-off numbers were determined by obtaining the largest value such that the tail probability is less than but closest to 0.05.

| Number enrolled (Y) | Stop/Investigate when number with events equals this number (X) | Probability of observing X or more events assuming $p=0.375$ | Number enrolled (Y) | Stop/Investigate when number with events equals this number (X) | Probability of observing X or more events assuming $p=0.375$ |
|---------------------|---|--|---------------------|---|--|
| 4 | 4 | 0.020 | 30 | 17 | 0.025 |
| 5 | 5 | 0.007 | 31 | 17 | 0.037 |

| | | | | | |
|----|----|-------|----|----|-------|
| 6 | 5 | 0.031 | 32 | 18 | 0.024 |
| 7 | 6 | 0.013 | 33 | 18 | 0.034 |
| 8 | 6 | 0.036 | 34 | 18 | 0.048 |
| 9 | 7 | 0.017 | 35 | 19 | 0.032 |
| 10 | 7 | 0.038 | 36 | 19 | 0.044 |
| 11 | 8 | 0.019 | 37 | 20 | 0.030 |
| 12 | 8 | 0.039 | 38 | 20 | 0.041 |
| 13 | 9 | 0.021 | 39 | 21 | 0.028 |
| 14 | 9 | 0.039 | 40 | 21 | 0.038 |
| 15 | 10 | 0.021 | 41 | 22 | 0.026 |
| 16 | 10 | 0.037 | 42 | 22 | 0.035 |
| 17 | 11 | 0.021 | 43 | 22 | 0.047 |
| 18 | 11 | 0.036 | 44 | 23 | 0.032 |
| 19 | 12 | 0.021 | 45 | 23 | 0.043 |
| 20 | 12 | 0.034 | 46 | 24 | 0.030 |
| 21 | 13 | 0.020 | 47 | 24 | 0.040 |
| 22 | 13 | 0.033 | 48 | 25 | 0.028 |
| 23 | 13 | 0.050 | 49 | 25 | 0.037 |
| 24 | 14 | 0.031 | 50 | 25 | 0.048 |
| 25 | 14 | 0.046 | 51 | 26 | 0.034 |
| 26 | 15 | 0.029 | 52 | 26 | 0.044 |
| 27 | 15 | 0.043 | 53 | 27 | 0.032 |
| 28 | 16 | 0.027 | 54 | 27 | 0.041 |
| 29 | 16 | 0.040 | | | |

In addition to the continual assessment of serious adverse events leading to permanent discontinuation from protocol, the DSMB may request for unblinded safety profile listings.

